## **Covariates**

Because the ultimate call to action (seeking care outside the ED) is likely to depend on proximity to the ED and alternate care options, all the regressions described above will include as covariates the driving distance in miles to the closest Geisinger ED and the driving distance in miles to the closest Geisinger urgent care location. Specifically, covariates will reflect the distance from the closest Geisinger ED and closest Geisinger urgent care location of the patient's zip code in the Geisinger electronic health records. Distances between each enrolled patient's zip code centroid and ED/urgent care locations will be computed using the same process described above in the section **Process for Determining a Patient's Nearest Urgent Care**, with the added step of computing the driving distance in miles for each zip code.

## **Primary Analysis Sample**

Analysis will be limited to patients who, at the time of enrollment, lived close enough to an urgent care location to be shown a map to a specific Geisinger urgent care location (i.e., those who lived within 40 miles, using the Haversine method, of a Geisinger urgent care clinic). We estimate that over 98% of patients will be included in this primary analysis. We will also run a sensitivity analysis that includes all patients.

## **Other Pre-specified Outcomes**

We will run the analyses described above on the following additional outcomes:

1. Urgent care visits

Visited urgent care (y/n)

[Time Frame: In the 30 days following the appointment]

2. Calls

Called Geisinger (y/n)

[Time Frame: In the 30 days following the appointment]

3. Patient portal messages

Sent a patient portal message (y/n)

[Time Frame: In the 30 days following the appointment]

## **Analysis Notes**

Recent work suggests that OLS regressions are appropriate in randomized experiments with binary outcome variables such as ours (Gomila, 2021).

In addition to the analyses described above, we may run sensitivity analyses such as using count or continuous variables instead of dichotomized variables.

An exploratory analysis will test whether any of the experimental arms perform better than baseline, using a dichotomous predictor variable (0 = standard practice, 1 = any modified AVS).

Finally, we plan to run exploratory analyses to understand heterogeneity in observed effects (e.g., in covariates such as age, sex, race, or frequency of exposure to the AVS).

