### Design

This study is a randomized controlled trial with 4 study arms. Patients will be randomized to receive or not receive a modified AVS after outpatient in-person or telehealth visits.

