### Methods

At the time of a patient's first qualifying appointment during the study period, patients will be randomized into the following study arms:

1. **Standard practice:** Patients in this arm will receive the current standard practice AVS.
2. **Contact us first:** Patients in this arm will receive the standard AVS, plus information on how to contact Geisinger if they need medical attention.
3. **Contact us first + urgent care map:** Patients in this arm will receive the standard AVS, plus information on how to contact Geisinger if they need medical attention, plus a map of their nearest Geisinger urgent care location and additional information about urgent care.
4. **Contact us first + urgent care map + self-triage:** Patients in this arm will receive the standard AVS, plus information on how to contact Geisinger if they need medical attention, plus a map of their nearest Geisinger urgent care location and additional information about urgent care. This arm will also receive a self-triage chart, with common reasons patients go to the ED and situations where seeking alternative care might be appropriate.

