### Sequential Design

We will use a group sequential design with O'Brien-Flemming alpha spending and beta spending (Lakens et al., 2021), with optional stopping for futility. We will perform one interim look after collecting data from 109,346 patients (50% of the sample) and the final look after

completing data collection with 218,692 patients. We will stop after the interim look if  $p < .005575$  (i.e., a much larger effect than expected) for the contrast between *any* of the 3 experimental arms and control in *Analysis 1* below. We may also stop for futility if  $z > -0.192$  (i.e., an effect in the opposite direction to our expectations) for *all* 3 contrasts between experimental arms and control in *Analysis 1* below. All tests will be 1-sided tests with an overall alpha of .05.

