## Project Status

All patients have been enrolled, but we have not extracted the final outcome data.

We ran an interim analysis on preliminary outcome data, as described above. Although effect sizes met our optional stopping for futility criteria ( $zs < -0.192$ ), we decided to keep running the study to be able to run all final analyses at full power.

We were unable to turn off the intervention immediately once reaching our target sample size, so we exceeded our preregistered sample size. Our final analyses will be based on the full list of patients enrolled until the intervention stopped. We will also run the primary outcome analyses on the subset of patients enrolled through the day we reached the preregistered sample size.

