## Statistical Analysis Plan

### Planned Analyses

**Primary Outcome:** Inappropriate ED visits (y/n) [Time Frame: In the 30 days following the appointment]

We will apply the NYU algorithm (Ballard et al., 2010) to determine whether an ED visit is inappropriate.

We will use one of the following two methods:

1. Epic tool: Geisinger is working to implement a tool in Epic that can automatically run the NYU algorithm and identify inappropriate (or "non-emergent") ED visits. If this tool is running prior to data analysis, we will use it to identify inappropriate ED visits for our primary outcome.
2. Custom code: If the Epic tool is not yet implemented prior to our data analysis, we will pull, for each ED visit, the primary ICD code for the visit and use custom code to determine whether the visit was inappropriate, following the methods described in Ballard et al. (2010) or the most up-to-date version of the algorithm we have access to at the time of data analysis.

**Question 1:** Do AVSs decrease inappropriate ED visits when including information about how to contact Geisinger if patients need care?

**Analysis 1 (Confirmatory):** We will test the hypothesis that each of the individual modified AVS versions decreases the likelihood patients will visit the ED in the 30 days following their visit. We will run an OLS regression including a categorical predictor variable coding for experimental arm (0 = standard practice arm, 1 = contact us first arm, 2 = contact us first + urgent care arm, 3 = contact us first + urgent care map + self-triage arm).

**Question 2:** Do AVSs decrease ED visits when including an urgent care map, beyond modified AVS version without an urgent care map?

**Analysis 2 (Exploratory):** We will run an OLS regression including only experimental arms with modified AVSs. We will include a predictor variable indicating whether each patient's AVS version includes a map (0 = no map, contact us first arm; 1 = map, contact us first + urgent care map arm and contact us first + urgent care map + self-triage arm).

**Question 3:** Do AVSs decrease ED visits when including a self-triage tool, beyond modified AVS versions without a self-triage tool?

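### Does the exploratory test of whether any modified AVS arm beats standard practice need changing because its 0/1 predictor estimates an average effect?

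*Combined protocol and SAP*

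**What the plan says.** The Design section sets out the trial: "This study is a randomized controlled trial with 4 study arms". One arm is standard practice. The other three are modified AVS versions, and according to Methods each adds content to the one before it.

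Under Planned Analyses, confirmatory Analysis 1 enters arm as a four-level factor: "We will test the hypothesis that each of the individual modified AVS versions decreases the likelihood patients will visit the ED". The Sequential Design section bases the interim efficacy rule on the same arm-by-arm contrasts, with a threshold that applies "for the contrast between *any* of the 3 experimental arms and control in *Analysis 1* below". It also makes all tests one-sided, with an overall alpha of .05.

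The Analysis Notes then add a supplementary, exploratory analysis to test "whether any of the experimental arms perform better than baseline, using a dichotomous predictor variable (0 = standard practice, 1 = any modified AVS". The question and the coding thus stand in one sentence. No decision, alpha, sample size or stopping rule is tied to it.

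Project Status says that "All patients have been enrolled, but we have not extracted the final outcome data", although an interim analysis on preliminary data has been run.

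**The concern.** A test of whether any of several arms works is usually built from the separate arm contrasts, for example from the largest of them. A single indicator for the three modified arms together does something else. It estimates how the modified arms do on average, so one good arm can be diluted by two that do nothing, or cancelled by two that do harm.

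The word is also used in two ways. In Sequential Design it points to separate contrasts, and in the Analysis Notes to a pooled group. A reader who carries the first meaning into the second place could take a null pooled result to mean that no version works, which the model cannot show. Unequal effects are plausible, since the Objectives ask which version is most effective and Analyses 2 and 3 ask what the map and the self-triage chart add.

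**Working it through.** **Inputs.** Rates of 3.88% and 3.50%, 215,000 patients for the fixed design, 95% power and one-tailed alpha .05 come from Power Analysis. That section also gives 218,692 patients after inflation by 1.01717. Allocation is not stated, so equal arms are assumed: 215,000/4 = 53,750, or 218,692/4 = 54,673. Covariates and the interim look are ignored. Effects are control minus modified, so a positive value is a benefit.

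**Step 1: the plan's own power.** For one arm against control with 53,750 each:

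- SE = √[(0.0388×0.9612 + 0.0350×0.9650)/53,750] = √(0.07107/53,750) = 0.001150
- Power = Φ(0.0038/0.001150 − 1.645) = Φ(1.66) = 95.2%

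This matches the stated 95%, so the design figure is for a single arm-versus-control contrast in equal arms. With 54,673 per arm it is 95.4%.

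**Step 2: what the pooled coefficient estimates.** With the modified arms coded 1 and equal allocation, the coefficient is (d1 + d2 + d3)/3, apart from covariate adjustment. The part of the concern that says it is an average is right.

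**Step 3: what a significant pooled result means.** If no arm is better than control, every d is zero or negative, and so is their mean. The one-sided test then rejects at most 5% of the time. Conversely, a mean above zero requires at least one d above zero. The pooled test is therefore a valid test of the null that no arm is better, and its rejection supports the claim in the label. It does not say which arm.

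**Step 4: what a null pooled result means.** With v = p(1−p) and n = 54,673:

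- SE = √[v0/n + (v1+v2+v3)/(9n)]
- Power = Φ(mean effect/SE − 1.645)

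With one arm at 3.50% and two at 3.88%, the mean effect is 0.38/3 = 0.127 points and the SE is 0.095 points. Power is Φ(1.333 − 1.645) = 37.8%.

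The table sets the pooled test beside a one-sided maximum test. The Dunnett critical value is 2.062 for a fixed design; a value of 2.14 allows for the interim look.

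| True effects in the three modified arms | Pooled | Maximum test, 2.062 / 2.14 |
|---|---|---|
| One at the design effect, two at zero | 37.8% | 90% / 88% |
| Zero, half and full design effect | 64% | 90% / 89% |
| One-third, two-thirds and full | 85% | 92% / 91% |
| Two at the design effect, one at zero | 84.9% | 97% / 96% |
| All three at the design effect | 99.2% | 98.3% / 97.8% |

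An extreme illustration: with one arm at 3.50% and two at 4.07%, the modified mean is (3.50 + 4.07 + 4.07)/3 = 3.88%. The pooled effect is zero, and the test rejects 5% of the time although one arm works.

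**Step 5: whether the plan relies on a pooled null.** It does not. No section says what would be concluded from one. The arm-specific question belongs to Analysis 1, where a single working arm has 95.4% power in its own contrast, against 37.8% in the pooled test.

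**The case for a change.** The strongest case for a change is that the window is still open and the cost is small. Final outcomes have not been extracted, one sentence would align label and model, and a single multiplicity-adjusted p-value from the Analysis 1 contrasts would answer the any-arm question directly. With one working arm, that test has about 90% power where the pooled one has 38%. Reading the any-arm answer from three unadjusted one-sided .05 contrasts would instead carry an 11.8% chance of at least one false positive.

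Part of this stands. The label is loose, a pooled null is weak evidence when effects differ, and the maximum test is clearly stronger in that case. The rest does not lead to a change here:

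- The two tests are both valid and trade power. Pooling is ahead by 0.9 to 1.3 points when all three arms work equally (99.15% against 98.25% or 97.82%). All three modified versions share the contact information, so asking about them together is a natural supplement. The 38% figure needs two of the three versions to do nothing, which the plan does not suggest.
- The 11.8% belongs to the Analysis 1 contrasts. The pooled test has an error rate of 5%. Whether Analysis 1 needs a multiplicity adjustment is a separate question and lends no weight to this one.
- A new any-arm test, added after an interim look and with a critical value that the plan does not contain, is a larger step than a loose label warrants.
- The two uses of the word do not collide. Sequential Design ties it expressly to the Analysis 1 contrasts, and the Analysis Notes define it by the coding.

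**Conclusion.** No change is needed. The predictor does estimate the average effect of the three modified AVSs, and the sentence would be more exact if it said so. But the coding is given beside the label, a significant one-sided result supports the labelled claim, and nothing in the plan rests on a non-significant one. Relabelling would move no estimate, p-value, sample size or stopping rule.

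What remains is a limit on interpretation. A pooled null has only 37.8% power behind it if a single arm reaches the design effect, rising to 84.9% for two arms and 99.2% for three, so conclusions about individual versions should come from Analysis 1. Analysts who read the coding will see this, and can describe the result as an average effect when they report it.

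The power figures assume equal arms of 54,673, 3.88% in the control arm, one-sided .05, no covariates and no interim look (except for the 2.14 critical value). Leaving out the roughly 2% of patients beyond 40 miles lowers each by less than 1 point. The validity argument in step 3 does not depend on equal arms: it needs only that each arm carries positive weight in the average.
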